1 PURPOSE/HYPOTHESES

1.1 Purpose

The purpose of this pilot study is to determine if Triheptanoin is safe and tolerable in people with ALS, and if it is associated with any promising changes in a clinical measure of disability or biomarkers of cellular energetics or oxidative stress.

1.2 Primary Hypothesis

The primary hypothesis is that Triheptanoin is associated with at least a 20% slowing in disability progression as measured by revised ALS functional rating scale (ALSFRS-R) in people with amyotrophic lateral sclerosis (PALS).

1.3 Secondary Hypotheses

Secondary hypotheses are as follows:

1. Triheptanoin favorably alters MR spectroscopy in PALS
2. Triheptanoin favorably alters serum and urinary biomarkers of mitochondrial function and oxidative stress in PALS
3. Triheptanoin is safe and well tolerated in PALS.

2 BRIEF BACKGROUND

Amyotrophic Lateral Sclerosis (ALS) is a degenerative motor neuron disease characterized by rapidly progressive disability and shortened survival (1). PALS lose about a point per month on a 48-point functional rating scale, and their median survival is 3 years from symptom onset (2). While symptomatic care has improved, there remains no treatment that can meaningfully slow ALS progression or prolong survival (1).

The causes of ALS are largely unknown. However, mitochondrial dysfunction, resulting in impaired energy production, oxidative stress and apoptosis, may play a key role in ALS progression (3). Triheptanoin can improve mitochondrial function and energy production and therefore has potential for slowing ALS progression (reviewed in reference 3). Indeed, triheptanoin slowed motor neuron loss and delayed the onset of weakness in a mutant SOD1 model of ALS (4).

3 DESIGN & PROCEDURES

3.1 Design Overview

This is an open label, prospective cohort study of 10 PALS from the Duke ALS Clinic (5). The first 5 enrolled PALS (Group 1) will receive standard ALS care for the first month, then standard care plus Triheptanoin for the next 5 months. The next 5 enrolled PALS (Group 2) will receive standard ALS care plus Triheptanoin for 6 months (Figure 1). All Group 1 and Group 2 PALS who complete this 6-month study will have an option for Triheptanoin treatment extension for an

additional 12 months. In addition to the PALS, there will also be 5 healthy controls enrolled (Group 3), people that do not have ALS or any other neurodegenerative disease). These participants will not receive any treatment; the only outcome measure they will complete is serum and urine biomarker testing at screening/baseline, month 1 and month 6 (Figure 1).

[figure not shown]

Figure 1: Study Treatment Schema

Human trials with Triheptanoin have demonstrated an excellent safety profile, with only rare associated gastrointestinal side effects (see the provided copy of Ultragenyx’s Investigator’s Brochure (IB) and references 6-9). However, it has never been studied in PALS. To mitigate the risks of rare gastrointestinal side effects, all our participants will be followed by a nutritionist for the duration of this study.

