3.3 Treatment Regimen

There will be 2 treatment Groups ([Figure 1](#)). Five PALS (Group 1) will be on standard care for 1 month, then standard care and Triheptanoin for 5 months. Five PALS (Group 2) will be on standard care and Triheptanoin for 6 months. The rationale for delaying triheptanoin treatment in one group is to look for differences in MR spectroscopy related to treatment at the 1 month time point. The target triheptanoin dose for this study is 1g/kg/d. This target dose was selected because it was safe and tolerable and altered brain MR spectroscopy in patients with Huntington's Disease (10). Participants will taper up to this dose as follows: start at 0.25g/kg/d for 1 week, then take 0.5g/kg/d for 1 week, then take 1g/kg/d and stay on this dose for the duration of the study. Triheptanoin will be administered orally with food or by gastrostomy tube over 3 divided doses (breakfast, lunch, and dinner). If at any point after week 1 a participant does not appear to be tolerating their current dose, it will be reduced by 0.25g/kg/d. If they cannot tolerate the starting dose of 0.25g/kg/d, the treatment will be discontinued. A dietician will make contact with all participants every month, either in person or by telephone, to try and maximize compliance. All PALS in Groups 1 and 2 who complete the 6-month trial, regardless of their MR spectroscopy results, will have the option for treatment extension for an additional 12 months.

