3.5.2 Secondary Outcome Measures

Secondary outcome measures include:

MR Spectroscopy NAA/Cr ratio in motor cortex will be measured at screening/baseline and 1 month time points. This measure declines over time in patients with ALS (14-17). This measure can respond to treatment; it was shown to improve over 3 weeks in patients with ALS on riluzole compared to a group that was not on this treatment (18). We will compare the MR spectroscopy changes over 1 month in Group 1 to the MR spectroscopy changes over 1 month in Group 2.

A Serum and Urine Biomarker Panel will be obtained at screening/baseline, 1 month and 6-month time points and analyzed using liquid chromatography/tandem mass spectrometry. Laboratory, pathologic, and epidemiologic evidence clearly supports the hypothesis that oxidative stress is central in the ALS pathogenic process, particularly in genetically susceptible individuals (19). Oxidative stress biomarkers in cerebrospinal fluid, plasma, and urine are elevated, suggesting that abnormal oxidative stress is generated outside of the central nervous system. Magnitude of lipid peroxidation, measured as non-enzymatic oxidation products of arachidonic acid, F2-isoprostanes, appears the most obvious oxidative stress marker. We will measure urine F2-isoprostane metabolites (class III: iPF2 α -III, and 2,3-dinor iPF-2 α -III, class VI: iPF-2 α -VI, and 8,12-iso-iPF-2 α -VI), urine creatinine, and serum and urine glutamate, α -keto-glutarate, NADH, coenzyme A levels in all treated participants and healthy controls at screening/baseline, month 1 and month 6 time points. We will compare the biomarker changes at different time points between Groups 1, 2 and 3.

For safety monitoring: concomitant medications, vital signs, weight, physical exam and safety labs (CBC, CMP, Lipid Profile, GGT, LFT and pregnancy testing for sexually active females with child bearing potential) will be measured at screening/baseline, 1 month, 3 month, and 6-month time points. Adverse events will be monitored continuously throughout the study, as described in Section 5.1.

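### Delayed or immediate start is set by enrolment order, so the month-1 MR spectroscopy comparison cannot separate triheptanoin from early versus late enrolment; a concealed random 5:5 list would fix this at little cost

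*Combined protocol and SAP*

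**What the plan says.** Section 3.1 (Design Overview) assigns the groups by order of entry: "The first 5 enrolled PALS (Group 1) will receive standard ALS care for the first month" and "The next 5 enrolled PALS (Group 2) will receive standard ALS care plus Triheptanoin for 6 months". The protocol describes no randomization, concealment, matching or adjustment for time of enrolment, and gives no reason for filling the groups in this order.

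Section 3.3 (Treatment Regimen) gives the purpose of the delay: "The rationale for delaying triheptanoin treatment in one group is to look for differences in MR spectroscopy related to treatment" at one month. Section 3.5.2 (Secondary Outcome Measures) sets the scan times, "MR Spectroscopy NAA/Cr ratio in motor cortex will be measured at screening/baseline and 1 month time points", and the analysis: "We will compare the MR spectroscopy changes over 1 month in Group 1 to the MR spectroscopy changes over 1 month in Group 2". For the healthy controls, Section 3.1 says that "the only outcome measure they will complete is serum and urine biomarker testing at screening/baseline, month 1 and month 6", so they are not scanned.

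Secondary hypothesis 1 in Section 1.3, that triheptanoin favourably alters MR spectroscopy, rests on this comparison.

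**The concern.** Comparing one-month changes removes stable differences in level between the groups. It does not remove anything that alters the one-month change itself. The protocol points to two such factors, and a third is a general hazard of serial imaging:

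- **Progression rate.** Section 3.5.2 says of NAA/Cr that "This measure declines over time in patients with ALS", and Section 3.6 assumes ALSFRS-R slopes that vary widely between patients (about 0.25 to 3.38 per month). Faster progressors in one group could produce a different one-month change.
- **Background treatment.** Section 3.2 admits patients on or off riluzole and Radicava. Section 3.5.2 says of NAA/Cr that "it was shown to improve over 3 weeks in patients with ALS on riluzole compared to a group that was not on this treatment".
- **Equipment.** A scanner or sequence change could fall between the two scans of some patients, all of them in one group.

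Because each assignment is known before the patient is approached, the time at which a given patient is enrolled could also be influenced by the start that he or she would receive.

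Five patients wait a month for treatment so that this comparison can be made. If a difference appears, the plan has no sound way to say whether it reflects the drug or who entered early and who entered late.

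**Working it through.** **Inputs.** From Section 3.1: 10 patients, positions 1–5 delayed and 6–10 immediate. From Section 3.5.2: outcome is the one-month change in NAA/Cr, 5 v 5. The documents give no sample size, SD, alpha or test for this contrast, so there is no planned figure to reproduce; Table 3 in Section 3.6 concerns ALSFRS-R slope only. Assumed for illustration: two-sided 5% t-test, 8 degrees of freedom, effects in SD units of the one-month change.

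**Step 1: aliasing.** Write the change as α + τ·(treated) + β·(later enrollee) + error. The two indicators are identical (correlation 1.0), so the design matrix has rank 2 for three columns and the contrast estimates τ + β. If enrolment is instead modelled as a straight-line trend over positions 1–10, its correlation with treatment is 0.87. Adjustment is then possible, but inflates the variance 4.1-fold (standard error √4.125 ≈ 2.0-fold) and depends on the assumed shape.

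**Step 2: what the change score removes.** With a steady instrument drift of g per month, a patient enrolled at time e has drift g(e+1) − g(e) = g, the same for everyone, so it cancels. A step change, or a difference in rate of change, does not.

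**Step 3: other scans.** Group 1 is never scanned on drug, since scans stop at month 1, and controls are not scanned. Group 2's own before/after change has no concurrent control.

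**Step 4: size under assumed non-drug differences, with no drug effect.** For a step d between groups, rejection comes from the noncentral t with noncentrality d·√(5/2). For a linear trend totalling T SD from patient 1 to patient 10, the mean positions are 3 and 8, so the group difference is 5T/9. For a 1 SD scanner step hitting k patients of one group, the bias is k/5.

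| Assumed non-drug effect | Bias in contrast | False positives, enrolment order |
|---|---|---|
| Step 0.25 SD | 0.25 SD | 6.4% |
| Step 0.5 SD | 0.5 SD | 10.8% |
| Step 1.0 SD | 1.0 SD | 28.6% |
| Trend, T = 0.5 SD | 0.28 SD | 6.6% |
| Trend, T = 1.0 SD | 0.56 SD | 11.6% |
| Trend, T = 1.8 SD | 1.0 SD | 25.6% |
| Scanner step, 1 patient | 0.2 SD | 4.9% |
| Scanner step, 2 patients | 0.4 SD | 6.9% |

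The trend and scanner rows come from simulation. In the cases also simulated under random 5:5 allocation (steps of 0.5 and 1.0 SD, all three trends, and the two-patient scanner step), the rate stays at about 5%.

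**Step 5: random 5:5 allocation.** There are C(10,5) = 252 equally likely lists. The expected difference between groups in mean enrolment position is 0 (SD 1.91), against a fixed 5.0 now. An exact first-five/last-five split has probability 2/252 = 0.8%; an early/late split of 4:1 or worse has probability (2 + 2·5·5)/252 = 20.6%. Assignments certain in advance fall from 10 of 10 to 10/6 = 1.7 on average. Someone tracking the list would still guess 5 + 2⁹/252 − 0.5 = 6.5 of 10 correctly, where chance is 5.

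**The case against.** The strongest reply is that the threat is hypothetical and the comparison is weak whatever is done.

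- **No early–late difference is shown.** All patients come from one clinic under one set of criteria. The slope range in Section 3.6 is a simulation assumption about spread between patients, on a different measure. The stable-dose rule of at least 30 days is longer than the 3-week riluzole response. No scanner change is mentioned, and one hitting a single patient has no visible effect on the error rate. This stands: the size of any bias is unknown, and the larger figures above need shifts that nothing in the documents establishes.
- **Imbalance would be visible.** Table 1 records disease characteristics, concomitant medications and ALSFRS-R at baseline, and Section 3.6 computes a pre-trial slope for every patient. This stands for progression rate and riluzole or Radicava use. But 10 patients do not allow useful adjustment, and unrecorded factors remain.
- **A rise in Group 2 could not be explained by rate of decline alone.** This is true, but an uncontrolled before/after rise is not the planned comparison, and it does not separate the drug from other influences in the same period.
- **The aliasing is partly definitional.** Period is defined by the same split as treatment. A smooth trend could be estimated, at the cost shown in Step 1.
- **Five per group is too few anyway.** Under randomization the 95% interval is still 2.306 × √(2/5) = ±1.46 SD, 80% power needs about 2.0 SD, and a given baseline covariate differs by more than 0.5 SD in 2·(1 − Φ(0.5/√0.4)) = 43% of lists. This stands as a limit on the gain. The difference is that chance imbalance is error that the interval covers, whereas sequential filling produces bias that it does not.

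**Conclusion.** The concern holds. As written, the month-1 MR spectroscopy contrast carries in full any non-drug difference in one-month change between early and late enrollees; under a random 5:5 list the expected bias is zero. That is a structural result and needs no assumption about MR spectroscopy variance. The false-positive rates are illustrations that rest on the assumed t-test, alpha and shift sizes.

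The reach is limited. The primary ALSFRS-R analysis compares each patient with his or her own pre-enrolment slope and does not use this contrast. The month-1 biomarker comparison shares the weakness to a lesser degree, because Group 1 also has an on-drug sample at month 6 and healthy controls are sampled. The change should be made because the delay was introduced for this one comparison and the remedy is cheap; it does not undermine the trial as a whole.

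**What to change.** In Section 3.1, replace allocation by enrolment order with wording such as:

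> The 10 PALS will be allocated at random, 5:5, to delayed start (Group 1) or immediate start (Group 2) from a single concealed list, held electronically and hidden from those who enrol patients. Each allocation will be opened only once eligibility is confirmed and the baseline scan and samples have been obtained.

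In Section 3.3, describe the two groups as randomly allocated. Group sizes, visits, scans and treatment periods stay as they are.

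**Cost.** A ten-line electronic list and a few sentences, with no added patients, visits or scans. There are two practical consequences. Patients will not know their start time when they consent. Because Table 1 dispenses drug to Group 2 at the screening/baseline visit, drug must be available at every such visit. Assessment remains open label, and the last assignments become predictable once one group is full, so the list should be held outside the recruiting team.

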3.2 Study Population

Participants will be patients in the Duke ALS Clinic that meet the following criteria.

Inclusion:

1. Lab supported probable or more definite ALS by El Escorial Criteria
2. Age greater than or equal to 18 years
3. Willing and able to provide informed consent
4. On riluzole at a stable dose for at least 30d or not taking this
5. On Radicava at a stable dose for at least 30d or not taking this
6. Life expectancy at least 6 months

7. Currently managed on a reasonably stable diet, avoidance of fasting, carnitine or medium chain triglyceride (MCT) oils
8. Must stop any other experimental ALS treatment for at least 30 days prior to screening
9. If sexually active, must agree to use contraceptive or abstinence for duration of treatment with triheptanoin
10. Females of child bearing age must have negative pregnancy test at screening

Exclusion:

1. Unwilling or unable to provide informed consent
2. Previous intolerance or adverse reaction to triheptanoin or MCT
3. Conditions that will prohibit MRI scanning (metal in eye, some surgical implants, claustrophobia, inability to lie supine)
4. Have any other co-morbid conditions that in the opinion of the study investigator, places the participant at increased risk of complications, interferes with study participation or compliance, or confounds study objectives

There will also be 5 healthy controls (adults without ALS or any other neurodegenerative disease) enrolled.

3.3 Treatment Regimen

There will be 2 treatment Groups ([Figure 1](#)). Five PALS (Group 1) will be on standard care for 1 month, then standard care and Triheptanoin for 5 months. Five PALS (Group 2) will be on standard care and Triheptanoin for 6 months. The rationale for delaying triheptanoin treatment in one group is to look for differences in MR spectroscopy related to treatment at the 1 month time point. The target triheptanoin dose for this study is 1g/kg/d. This target dose was selected because it was safe and tolerable and altered brain MR spectroscopy in patients with Huntington's Disease (10). Participants will taper up to this dose as follows: start at 0.25g/kg/d for 1 week, then take 0.5g/kg/d for 1 week, then take 1g/kg/d and stay on this dose for the duration of the study. Triheptanoin will be administered orally with food or by gastrostomy tube over 3 divided doses (breakfast, lunch, and dinner). If at any point after week 1 a participant does not appear to be tolerating their current dose, it will be reduced by 0.25g/kg/d. If they cannot tolerate the starting dose of 0.25g/kg/d, the treatment will be discontinued. A dietician will make contact with all participants every month, either in person or by telephone, to try and maximize compliance. All PALS in Groups 1 and 2 who complete the 6-month trial, regardless of their MR spectroscopy results, will have the option for treatment extension for an additional 12 months.

3.4 Trial Procedures and Assessments

The intervention being studied is treatment with Triheptanoin. The procedures and assessments being performed include consent, screening for inclusion and exclusion criteria, dispensing study drug for consented patients who pass screening, obtaining vital signs, obtaining demographics and disease characteristics, obtaining weight, performing a brief physical and neurological exam, adverse event monitoring, review of concomitant medications, safety labs, pregnancy testing, ALSFRS-R, MRI spectroscopy, serum and urine biomarkers of energetics and oxidative stress.

The schedule for these procedures are outlined in [Table 1](#), and a description of why they are important, are provided in the Outcome Measures in [Section 3.5](#).

Table 1: Schedule of Events for Group 1 and 2

	Screening/ Baseline Visit	Month 1 Visit	Month 2 Phone Call	Month 3 Visit	Month 4 Phone Call	Month 5 Phone Call	Month 6 Visit	Extension Month 6 and 12 Phone Calls
Consent	X							
Inclusion/ Exclusion	X							
Dispense Drug	(Group 2 only)	X		X			X	
Vitals	X	X		X			X	
Demographics and Disease Characteristics	X							
Weight	X	X		X			X	
Physical Exam	X	X		X			X	
Adverse Event Monitoring*	X	X	X	X	X	X	X	X
Con Meds	X	X	X	X	X	X	X	
Neuro Exam	X	X		X			X	
Safety Labs	X	X		X			X	
Pregnancy Test	X	X					X	
ALSFRS-R	X	X	X	X	X	X	X	X
MRS	X	X						
Serum and Urine Biomarkers	X	X					X	

	Screening/ Baseline Visit	Month 1 Visit	Month 2 Phone Call	Month 3 Visit	Month 4 Phone Call	Month 5 Phone Call	Month 6 Visit	Extension Month 6 and 12 Phone Calls
Dietician Contact (may be in person or telephone)	X	X	X	X	X	X	X	

*Adverse event screening will be captured throughout the protocol and the extension period, and continue for an additional 4 weeks following the last dose of study medication.

Table 2: Schedule of Events for Group 3

	Screening/Baseline Visit	Month 1 Visit	Month 6 Visit
Consent	X		
Serum and Urine Biomarkers	X	X	X

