5 SAFETY & ADVERSE EVENTS

5.1 Adverse Events Monitoring

All adverse events (AEs), whether observed by the Investigator, elicited from the participant or volunteered by the participant, and whether ascribed to the drug or not, will be recorded. This will include the following: a brief description of the event, the date of onset, the date of resolution, the duration and type of the event, the severity, contributing factors and any action taken with respect to the study drug. This recording will commence following informed consent, and with the initiation of protocol-specific procedures and continue at each study visit or telephone contact until 4 weeks following the last study related visit.

For each adverse event, the relationship to the study drug will be recorded as one of the choices on the following scale:

DEFINITE Causal relationship is certain (i.e., the temporal relationship between drug exposure and the adverse event onset/course is reasonable, there is a clinically compatible response to de-challenge, other causes have been eliminated and the event must be definitive pharmacologically or phenomenologically using a satisfactory re-challenge procedure if necessary).

PROBABLE High degree of certainty for causal relationship (i.e., the temporal relationship between drug exposure and the adverse event onset/course is reasonable, there is a clinically compatible response to de-challenge [re-challenge is not required] and other causes have been eliminated or are unlikely).

POSSIBLE Causal relationship is uncertain (i.e., the temporal relationship between drug exposure and the adverse event onset/course is reasonable or unknown, de-challenge/re-challenge information is either unknown or equivocal and while other potential causes may or may not exist, a causal relationship to the study drug does not appear probable).

UNLIKELY Not reasonably related, although a causal relationship cannot be ruled out (i.e., while the temporal relationship between drug exposure and the adverse event onset/course does not preclude causality, there is a clear alternate cause that is more likely to have caused the adverse event than the study drug).

NOT RELATED No possible relationship (i.e., the temporal relationship between drug exposure and the adverse event onset/course is unreasonable or incompatible, or a causal relationship to study drug is implausible).

The severity of each adverse event must be recorded as one of the choices on the following scale:

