5.2 Data & Safety monitoring

Adverse events will be continuously tracked throughout the study as described above and below. There is no formal safety monitoring plan or DSMB, nor are there any formal stopping rules. Patients who do not tolerate triheptanoin (as described in Section 3.3) will be encouraged to continue in the protocol off-treatment. PI will review and sign off on all adverse events and promptly report these to the IRB.

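### The promised 4-week adverse-event window after dosing contains no scheduled contact for completers, and seldom one for participants who stop during the extension

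*Combined protocol and SAP*

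**What the plan says.** Two places define how long adverse events are collected. The footnote to Table 1 (section 3.4) covers the protocol and the extension, and says screening will then "continue for an additional 4 weeks following the last dose of study medication". Section 5.1 says recording will "continue at each study visit or telephone contact until 4 weeks following the last study related visit". The first counts from the last dose, the second from the last visit.

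Section 5.1 accepts events by any route: "whether observed by the Investigator, elicited from the participant or volunteered by the participant".

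On dosing, section 3.3 says "Five PALS (Group 2) will be on standard care and Triheptanoin for 6 months"; Group 1 starts a month later and also finishes at month 6. Participants who complete the 6 months "will have the option for treatment extension for an additional 12 months".

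On contacts, Table 1 marks adverse event monitoring at baseline, at every month from 1 to 6, and at the column headed "Extension Month 6 and 12 Phone Calls". There is no later column.

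Section 5.2 adds that participants who do not tolerate the drug "will be encouraged to continue in the protocol off-treatment".

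**The concern.** Section 5.1 says that events are recorded at contacts. If the last contact falls on the same nominal day as the last dose, a 4-week window that opens on that day has no contact in it. The plan states a period of collection but schedules no occasion for collecting.

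Safety and tolerability are part of the purpose (section 1.1) and form the third secondary hypothesis (section 1.3). Section 3.1 says the drug has not been studied in ALS before, and section 5.2 says there is no formal safety monitoring plan or DSMB. With 10 treated participants, one affected participant who goes unrecorded moves an observed proportion by 1/10, or 10 percentage points. A reader who sees a 4-week post-dose window would assume that participants were asked about events during it.

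**Working it through.** The plan gives no figure to reproduce here. The check sets the contact schedule against the dosing schedule.

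**Inputs**
- Contacts with adverse event monitoring (Table 1), in months from baseline: 0, 1, 2, 3, 4, 5, 6, then 12 and 18 (extension months 6 and 12).
- Nominal end of dosing (section 3.3): month 6 without the extension, month 18 with it.
- Window: 4 weeks = 28 days (Table 1 footnote, section 5.1).
- Conversion: 1 month = 365.25/12 = 30.44 days.
- Assumptions: stop dates of early stoppers are uniform over the period concerned, and early stoppers keep their scheduled contacts.

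**Completers: is there a contact after the last dose and within 28 days?**
- No extension: last dose on day 6 × 30.44 = 182.6; window closes on day 210.6. Contacts inside: 0.
- Extension completed: last dose on day 18 × 30.44 = 547.9; window closes on day 575.9. Contacts inside: 0.

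The section 5.1 anchor does not change this. Without the extension, the last visit is the month 6 visit and nothing is scheduled in the next 28 days. With the extension, the last study visit could be read as the month 6 visit, because the extension contacts are calls, or the final call could be counted as a visit. Neither reading puts a contact in the following 28 days.

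**Early stoppers: share of stop dates with a contact within 28 days**

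Share = 28 / (days between contacts).
- Main study, monthly contacts: 28 / 30.44 = 92%.
- Extension, calls 6 months apart: 28 / (6 × 30.44) = 28 / 182.6 = 15%.

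**Size of the unelicited window, upper limit**
- All 10 treated participants: 10 × 28 = 280 days; 280 / 30.44 = 9.2 patient-months.
- On-drug time if nobody extends: 5 × 5 + 5 × 6 = 55 patient-months; 9.2 / 55 = 17%.
- On-drug time if all 10 complete the extension: 55 + 10 × 12 = 175 patient-months; 9.2 / 175 = 5%.

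**The case against.** The best defence is that the obligation is stated and only its logistics are absent. The footnote belongs to the adverse event row of the schedule, and screening suggests asking rather than waiting. Sections 3.5.2 and 5.2 describe monitoring or tracking as continuous, and a call log or manual could supply the contact. Part of this stands: the commitment is there. But section 3.5.2 refers to section 5.1, which relies on visits and calls; section 5.2 names no mechanism; and the documents mention no such log or manual.

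The dietician might seem to fill the gap: "A dietician will make contact with all participants every month, either in person or by telephone, to try and maximize compliance". The stated aim is compliance, however, and Table 1 marks this contact only through month 6.

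It is also fair that the missing contact affects neither the primary analysis nor the on-treatment safety data of the 6-month study, and that early stoppers in the main study are largely covered.

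Some stronger readings are tempting, but the documents do not support them:
- A reader might infer that post-dose events can surface only if volunteered, and so would be missed. Section 5.1 also counts events observed by the investigator, and participants are patients of the same clinic, so routine care may reveal some. What is absent is scheduled elicitation.
- A reader might infer a particular hazard from withdrawal or delayed toxicity. The documents describe neither; section 3.1 mentions rare gastrointestinal effects.
- A reader might infer that the final report will claim 4 weeks of complete follow-up. No text says so.
- A reader might take 17% as the size of the gap. That ratio holds only if nobody extends.

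**Conclusion.** The point holds as a mismatch between a stated collection window and the contact schedule. Completers have zero scheduled contacts in the 28 days after the last dose, with or without the extension and under either anchor. Participants who stop during the extension have one for only about 15% of stop dates; those who stop in the main study and stay in follow-up have one for about 92%.

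The unelicited time is at most about 9.2 patient-months, or between 5% and 17% of planned on-drug time depending on uptake of the extension. This upper limit takes all 10 participants to have an uncovered window. The shares for early stoppers depend on uniform stop dates and on participants keeping their scheduled contacts. Table 1 gives no visit windows, so last dose and last contact coincide only nominally; a late visit could fall a few days into the window.

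This is a gap in safety ascertainment that should be closed because safety is a stated aim and closing it is cheap. It does not threaten the primary analysis.

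**What to change.** Reconcile Table 1, its footnote and section 5.1:
1. Use one anchor for the 4-week window in both places. At present one counts from the last dose and the other from the last study visit.
2. Add to Table 1 one scheduled telephone contact at the end of that window, at which adverse events are asked about. It should apply to every treated participant, whether dosing ends early, at month 6, during the extension or at its end.

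The cost is one table column and about 10 short calls, one per treated participant.

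If no contact is added, the plan should say that events after the last dose are not actively elicited, and the 4 weeks should not be described as active follow-up.
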